## 7. Contraception provisions:

**Females:** Due to the teratogenic potential of LEN, FCBP must follow the rules listed below (otherwise excluded):

### **Applicable in all countries except the US:**

- a. Not be pregnant as confirmed by a negative serum pregnancy test at screening and a medically supervised urine pregnancy test prior to starting study therapy
- b. Refrain from breast feeding and donating oocytes during the study and for 3 months after the last dose of study drug or according to local guidelines for LEN, whichever is longer
- c. Agree to ongoing pregnancy testing during the course of the study, and after study treatment has ended. This includes pregnancy testing and counseling if a patient misses her period or if there is any abnormality in her menstrual bleeding and applies even if the patient practices complete sexual abstinence
- d. Commit to continued abstinence from heterosexual intercourse if it is in accordance with her lifestyle (which must be reviewed on a monthly basis) or agree to use and be able to comply with the use of highly effective contraception without interruption at least 4 weeks prior to start of study drugs, during the study treatment and for 3 months after the last dose of study drug, or, for LEN, according to the local guidelines, whichever is longer

### **Applicable in the US:**

- e. Not be pregnant as confirmed by pregnancy tests performed before treatment initiation, within 10–14 days and again within 24 hours of initiating treatment (even if true abstinence is the chosen method of birth control)
- f. Refrain from breast feeding and donating oocytes during the study and for 3 months after the last dose of study drug, or according to US guidelines for LEN, whichever is longer
- g. Agree to ongoing pregnancy testing during the study (every 4 weeks in women with regular menstrual cycle and every two weeks in women with irregular menstrual cycle), and after study therapy has ended (even if true abstinence is the chosen method of birth control). This includes pregnancy testing and counseling if a patient misses her period or if there is any abnormality in her menstrual bleeding
- h. Not get pregnant while taking the study treatment and for at least 3 months after the last dose of study treatments by using at the same time 2 effective methods of contraception, at least one highly effective method and one additional effective method (see [Appendix 13: Contraceptive Guidance and Collection of Pregnancy Information](#)), each time engaging in sexual activity with a male, starting at least 4 weeks before taking the study treatment, while taking the study treatment, during breaks (dose interruptions) and for at least 3 months after stopping the study treatment, or for LEN, according to the US guidelines, whichever is longer. True abstinence from heterosexual sexual intercourse is also an acceptable method of contraception. The use of emergency contraception is also permitted

8. Due to teratogenic potential of lenalidomide, male participants must follow the rules listed below (otherwise excluded):

**Applicable in all countries except the US:**

- a. Use an effective barrier method of contraception without interruption if the patient is sexually active with a FCBP. Male patients should refrain from donating sperm during the study participation and for 3 months after the last dose of study treatment, or according to the local guidelines for LEN, whichever is longer

**Applicable in the US:**

- b. Use a latex or synthetic condom each time they have sex with a FCBP. True abstinence from heterosexual sexual intercourse is also an acceptable method of contraception. The use of emergency contraception is also permitted. Male patients should refrain from donating sperm during the study participation and for 3 months after the last dose of study drug, or according to the US guidelines for LEN, whichever is longer

### 6.3 Screen Failures

Screen failures are defined as patients who consent to participate in the clinical study but are not subsequently entered into the treatment period. A minimal set of screen failure information is required to ensure transparent reporting of screen failure patients. This includes:

- Informed consent
- Inclusion/exclusion criteria
- Reason for screen failure (e.g., withdrawal of informed consent, death, etc.)
- Demography
- AEs (only if the patient experienced an SAE between signing the ICF and date of screen failure)

Patients can be re-screened at the discretion of the investigator under certain circumstances. Re-screening is restricted to one attempt per patient and can only be performed if one of the following criteria is met:

- The patient has already consented and met all of the inclusion and none of the exclusion criteria and his or her enrollment was delayed due to an unexpected event
- The patient previously failed to be eligible due to any event (e.g., planned surgery, laboratory test result) that has been resolved
- The patient previously failed screening but has become eligible for the study based on a change in the inclusion and exclusion criteria as the result of a protocol amendment
- The patient failed screening due to non-progressed / non-relapsed disease at the time of screening and is later clinically diagnosed as having progressed/relapsed
- A patient should only be rescreened if there is a clear indication that the patient may be eligible according to the currently valid study protocol

The following procedures should be performed for re-screened patients:

- The patient must sign and date a new ICF as part of the re-screening procedure
- The eligible patient will receive a new unique identification number
- A new electronic case report form (eCRF) should be completed
- The patient will be documented as rescreened in the source documents and eCRF

A rescreened patient can be enrolled, if all of the current inclusion criteria are met and none of the exclusion criteria are met.

## 7 STUDY TREATMENT(S)

### 7.1 Investigational Medicinal Products Administered

Tafasitamab must be handled and/or prepared as described in the Drug Handling Manual, the IB for tafasitamab, and other safety-relevant documents (e.g., Summary of Product Characteristics (SmPC) for the European Medicines Agency (EMA) or the Prescribing Information (PI, US FDA) for LEN). Tafasitamab will be administered in combination with LEN 25 mg [REDACTED] as shown in [Figure 2](#), [Figure 3](#), and [Table 9](#).

**Table 9: Overview of IMPs in MINDway**

IMP Name	Tafasitamab	LEN
Formulation	Vial	Capsule
Unit Dose Strength(s)/Dosage Level(s)	200 mg	25 mg 10 mg 5 mg
Route of Administration	i.v.	Oral

Abbreviations: i.v.=intravenous; LEN=lenalidomide.

On days when both study drugs are given together, LEN should be administered prior to tafasitamab.

#### 7.1.1 Tafasitamab (IMP)

Tafasitamab will be centrally supplied. Tafasitamab must be stored under 2° C to 8° C in its original package in an appropriate storage facility accessible only to the pharmacist(s), the investigator, or a duly designated person.

Tafasitamab is a lyophilizate supplied in single-use 20 mL glass vials. Each vial contains 200 mg of tafasitamab for reconstitution with 5 mL of water for injection (WFI). Reconstitution yields 40 mg/mL tafasitamab in 25 mM sodium citrate, 200 mM trehalose and 0.02% weight by volume (w/v) polysorbate 20 at pH 6.0. Reconstituted tafasitamab will be diluted into an infusion bag of 0.9% w/v sodium chloride solution for injection according to the description given in the Drug Handling Manual. The solution after reconstitution is colorless to slightly yellow and essentially free of foreign particles; it may contain a few white to whitish product-related particles.

The individual tafasitamab infusion will be prepared under aseptic conditions and administered at the study site, according to the directions of the sponsor, which will be provided in a Drug Handling Manual. In general, a vial of tafasitamab must be used as soon as possible after

reconstitution with WFI. After dilution for infusion, administration of tafasitamab should take place as soon as possible. Maximum allowed storage times and conditions will be detailed in the Drug Handling Manual.

Tafasitamab will be administered i.v. as per schedule of assessment and dosing scheme, respectively (see [Section 2](#) and [Table 5](#)).

Tafasitamab should **NOT** be administered as an i.v. push or bolus but as an i.v. infusion.

In the first 28-day cycle (Cycle 1) tafasitamab is given on Day 1, Day 4 and Day 8 at a dose of 12 mg/kg to mitigate the risk of IRRs and TLS.

Body weight will be measured on Day 1 of each cycle. This baseline-weight can be used to calculate the tafasitamab dose during the given cycle provided the weight does not deviate more than  $\pm 10\%$  from baseline during the course of this cycle. Using actual body weight measured prior to the particular tafasitamab infusion on visits other than Day 1 of the cycle is also allowed for dose calculation, if this is preferred by investigators.

In cases where the patient's body weight changes more than  $\pm 10\%$  from weight measured on Day 1 of the cycle, the current weight, measured 24 hours prior to the particular tafasitamab infusion must be used to calculate the tafasitamab dose.

Guidance on the infusion duration for each visit is summarized [REDACTED] Further details on the infusion rates are provided in the drug handling manual. If required, the investigator should use clinical judgement to optimize patient safety by administering the infusion more slowly.

[REDACTED]

Additionally, further guidance on infusion rate modifications for subsequent administrations in case of IRRs Grade  $\geq 3$  is summarized in [Table 11](#) below.

Please note that general management of IRRs is described in [Section 7.3.1](#).

**Table 11: Infusion Rate Modifications for Tafasitamab Infusion ( ) in Case of IRR's, Cytokine Release Syndrome (CRS)**

Infusion related reaction, Cytokine release syndrome	Infusion Rate
IRR Grade 3 and/or Grade 2 CRS during Cycle 1	If IRR Grade 3 and/or Grade 2 CRS in Cycle 1 has resolved and no further IRR Grade $\geq 3$ events are observed in cycle 2 and 3, the patient may receive tafasitamab with shorter infusion time from Cycle 4 Day 1 onward at the discretion of the investigator
IRR Grade 3 and/or Grade 2 CRS during any other Cycle	If IRR Grade 3 and/or Grade 2 CRS has resolved, tafasitamab administrations must be given at regular infusion rate i.e. approximately 4 hours in the current and subsequent Cycle. If the patient experiences no further IRR Grade $\geq 3$ , they may receive the tafasitamab administration with short infusion time from the next but one cycle onward at the discretion of the investigator.
IRR Grade 4 and/or Grade 3 CRS, Grade 4 CRS	Tafasitamab administration should be permanently discontinued.

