## 5.2 Data and Safety Monitoring Committee

A data and safety monitoring committee (DSMC), consisting of Sponsor representatives and investigators, will continuously monitor the study and can recommend to stop enrollment at any time based on emerging safety data and pre-defined stopping rules. In addition, pre-defined DSMC meetings will take place when 6 patients have completed the 5-week safety observation period (35 days from C1D1 onwards) [REDACTED] respectively.

Details of specific responsibilities, composition, meeting formats and frequency of the DSMC are outlined in the Data Safety Monitoring Committee Charter.

A recommendation [REDACTED]  
[REDACTED]  
[REDACTED]  
[REDACTED]  
[REDACTED]

The DSMC recommendations will be guided by pre-defined safety criteria that apply to the safety observation window of 35 days (from Cycle 1 Day 1 to Cycle 2 Day 7).

Pre-defined safety criteria (stopping rules):

- [REDACTED]
- [REDACTED]
- [REDACTED]

The pre-defined safety events are the following according to CTCAE version 5:

- Grade 4 or higher non-hematologic AE
- Grade 4 or higher neutropenia lasting > 7 days, despite standard of care treatments (i.e. G-CSF, others as needed)
- Grade 4 or higher anemia
- Grade 3 or higher neutropenia with associated fever (> 38.3 °C) lasting > 7 days, despite standard of care treatments (i.e. anti-infectives, G-CSF, others as needed)
- Grade 3 or higher IRR
- Grade 3 or higher TLS
- Grade 3 or higher thrombocytopenia with clinically significant bleeding
- CRS Grade 2 or higher

Events that are clearly attributed to the underlying disease or LEN alone will be discussed at the DSMC and a decision will be made whether these events should be considered as a pre-defined safety event.

If the safety results [REDACTED]  
[REDACTED]  
[REDACTED] in approximately 45 patients in total.

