**7.3.1.3 Interventions for Grade 3 IRRs, Grade 2 CRSs**

If a patient presents with a grade 3 IRR or grade 2 CRS:

- The infusion should be stopped immediately
- The patient must receive appropriate treatment with an antihistamine and/or acetaminophen (paracetamol) or methylprednisolone (or equivalent) and, if necessary, further medications (i.e. epinephrine, bronchodilator) as clinically indicated
- Only after the complete resolution of all symptoms, and after having received appropriate prophylactic medication(s), the infusion may be resumed at an infusion rate of 25% of the speed so far. If, after 1 hour, the patient's symptoms do not return and vital signs are stable, the infusion rate may be increased to a maximum of 50% of the baseline speed
- If, after the resumption of the infusion, symptoms return (irrespective of grade), the infusion must be stopped immediately and the infusion tubing should be disconnected from the patient
- Based on the investigator's decision the patient may receive further infusions of tafasitamab provided clinically appropriate precautions are undertaken. Pre-medication should be given before all subsequent infusions of tafasitamab throughout the study

If precluded from further tafasitamab administrations, the patient may continue treatment with lenalidomide.

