10.2.1.5. Predefined Safety Events

The following are predefined safety events according to CTCAE v5 for the safety observation window (35 days from Cycle 1 Day 1):

- Grade 4 or higher nonhematologic AE
- Grade 4 or higher neutropenia (PTs: neutropenia and neutrophil count decreased) lasting > 7 days despite standard of care treatments (eg, G-CSF)
- Grade 4 or higher anemia
- Grade 3 or higher neutropenia (PTs: neutropenia and neutrophil count decreased) with associated fever (> 38.3°C) lasting > 7 days despite standard of care treatments (eg, anti-infectives, G-CSF)
- Grade 3 or higher IRR (as per eCRF)
- Grade 3 or higher TLS (PT: tumour lysis syndrome)
- Grade 3 or higher thrombocytopenia (PTs: platelet count decreased and thrombocytopenia) with clinically significant bleeding
- Grade 2 or higher CRS (PTs: cytokine release syndrome and cytokine storm)

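### Table 11's conditions for returning to the short tafasitamab infusion name only IRR Grade ≥3, although Grade 2 CRS is an equal trigger (minor wording point)

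*Protocol*

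**What the plan says.** Table 11 in Protocol 7.1.1 covers both infusion-related reactions and cytokine release syndrome.

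- **Row 1** (Grade 3 IRR and/or Grade 2 CRS in Cycle 1): "If IRR Grade 3 and/or Grade 2 CRS in Cycle 1 has resolved and no further IRR Grade" ≥3 is seen in Cycles 2 and 3, the short infusion may be used from Cycle 4 Day 1 at the investigator's discretion.
- **Row 2** (the same triggers in any other cycle): "tafasitamab administrations must be given at regular infusion rate i.e. approximately 4 hours in the current and subsequent Cycle". After that, "If the patient experiences no further IRR Grade" ≥3, "they may receive the tafasitamab administration with short infusion time from the next but one cycle onward at the discretion of the investigator".
- **Row 3** (Grade 4 IRR, or Grade 3 or 4 CRS): tafasitamab stops for good.

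The sentence introducing the table also mentions only IRRs of Grade 3 or higher.

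Elsewhere the two trigger events are paired. Protocol 7.3.1.3 gives them a single set of interventions: "If a patient presents with a grade 3 IRR or grade 2 CRS". Protocol 5.2 lists both "Grade 3 or higher IRR" and "CRS Grade 2 or higher" as pre-defined safety events. SAP 10.2.1.5 does the same, with "Grade 2 or higher CRS (PTs: cytokine release syndrome and cytokine storm".

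SAP 6.4.2.4.3 gives the standard duration at 24 and 30 mg/kg as about 4 hours from Cycle 1 Day 15 to Cycle 3 Day 15, and about 2 hours from Cycle 4 Day 1.

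**The concern.** Both events start the restriction, but only one of them, on recurrence, stops its release. No visible text gives a reason for leaving CRS out. Under Table 12, Grade 2 CRS is hypotension that responds to fluids or hypoxia that responds to less than 40% oxygen, and one grade higher ends tafasitamab treatment. A site following row 1 to the letter could therefore give a patient with repeated Grade 2 CRS the faster infusion at Cycle 4 Day 1, while withholding it from a patient with repeated Grade 3 IRR. At stake is a small patient-safety inconsistency in a dosing rule.

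**Working it through.** The plan states no figure to reproduce. The check applies the two rows to each recurrence pattern after a Cycle 1 trigger.

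**Inputs.** Row 1 releases at Cycle 4. Row 2 requires about 4 hours in the event cycle k and in k+1, and releases at k+2. Durations and volumes come from SAP 6.4.2.4.3. Infusion days (Days 1 and 15 in Cycles 2 and 3, Day 1 from Cycle 4) are inferred from the visit schedule and that section, because the dosing table is redacted.

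**Assumptions.** When both rows apply, the more restrictive governs. A new event in Cycle 2 or later starts row 2 afresh.

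**Is the short infusion allowed at Cycle 4 Day 1?**

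| Recurrence | Row 1 | Row 2 | Result as written | Result with CRS named |
|---|---|---|---|---|
| Grade 3 IRR, Cycle 2 | no | yes (2+2 = 4) | no | no |
| Grade 3 IRR, Cycle 3 | no | no (3+2 = 5) | no | no |
| Grade 2 CRS, Cycle 2 | yes | yes (2+2 = 4) | **yes** | **no** |
| Grade 2 CRS, Cycle 3 | yes | no (3+2 = 5) | no | no |

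Among these four patterns, the omission changes the answer for Grade 2 CRS in Cycle 2. After a Cycle 2 event, row 2 requires 4 hours in Cycles 2 and 3, which is already the standard duration at the higher doses. Row 1's no-recurrence clause is then the only part of the table that could hold Cycle 4 Day 1 back, and that clause omits CRS.

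**Effect on the infusion.** For 250 mL, 250/4 = 62.5 mL/h becomes 250/2 = 125 mL/h. For 500 mL, 500/4 = 125 mL/h becomes 500/2 = 250 mL/h. The rate doubles.

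**Timing.** With 28-day cycles, Cycle 2 Day 1 is study day 29, Cycle 2 Day 15 is day 43 and Cycle 4 Day 1 is day 85. The faster infusion comes 85 − 43 = 42 to 85 − 29 = 56 days after a reaction to a Cycle 2 infusion.

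**Sensitivity to the reading.**

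- If only the row for the latest event governs, the omission changes nothing.
- If row 1 alone governs after a Cycle 1 event, Grade 2 CRS in Cycle 3 is missed as well.
- If each event keeps its own no-recurrence condition, two CRS events within Cycle 2, or within Cycle 3, also give a different release cycle.
- If failing a release condition bars the short infusion permanently, a Cycle 3 recurrence also differs, from Cycle 5 onward.

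**The case against.** The strongest objection is that the consequence depends on a precedence rule that the protocol does not contain. If the latest event's row simply replaces the earlier one, a Cycle 2 event of either type leads to discretionary release at Cycle 4, and IRR and CRS are treated alike. This stands as a limit on the claim. It is the less natural reading, however, because it would leave row 1's explicit condition about Cycle 2 without effect. Row 2's duty is also mandatory where row 1's release is only permissive.

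A second objection is that IRR Grade ≥3 is shorthand for both events, since the lead-in uses it for a table that plainly covers CRS. That is possible. But the trigger wording in the same rows names both events, so a site has no reason to read CRS into the release condition.

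Third, the infusion-duration guidance in Protocol 7.1.1 is redacted, Table 11's title contains a blank, and the drug handling manual is not among the documents. Any of these might settle the matter.

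Fourth, there are real safeguards. In the affected pattern, Cycle 3 must first pass at about 4 hours without a new trigger. Release is discretionary, slower infusion is always allowed, 7.3.1.3 requires pre-medication before every later infusion, and higher-grade CRS ends treatment. A patient whose first trigger falls in Cycle 2 also gets the same Cycle 4 release. All of this stands and keeps the point minor. Discretion is only a backstop, though, and for Grade 3 IRR the protocol did not rely on it alone.

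A reader might go further and infer that recurrent Grade 2 CRS is generally unprotected. Under the more restrictive row it is not: row 2 catches a recurrence in Cycle 3 or later. Nor is safety monitoring weakened, because Protocol 5.2 and SAP 10.2.1.5 both count Grade 2 CRS.

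**Conclusion.** The wording is inconsistent and worth correcting as a minor point. As written, a Cycle 1 trigger followed by Grade 2 CRS in Cycle 2 permits a roughly 2-hour infusion at Cycle 4 Day 1, while Grade 3 IRR in Cycle 2 does not. This rests on the more restrictive row applying; other readings would change more sequences or none, so the single pattern should not be presented as the only possible one.

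The number of patients is not estimable. A reader might build a figure from L-MIND (Protocol 3.3.3, Table 7), where 5 of 81 patients had tafasitamab-related IRR and CRS is not listed at the 3.0% threshold. Those counts are for any grade and any cycle at 12 mg/kg, they give no recurrence rate, and Protocol 7.1.3 warns of a possibly higher IRR risk at higher doses. The documents also do not say how many patients have yet to reach Cycle 4 Day 1; if none, the correction is only clerical. No endpoint, DSMC criterion or planned analysis is affected.

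**What to change.** In row 1, make release conditional on *no further IRR Grade ≥3 or CRS Grade ≥2*. Use the same words in row 2 and add CRS to the lead-in sentence for consistency; the row 2 edit changes little in practice, since a further Grade 2 CRS is itself a new row 2 event. State that the more restrictive row applies when both are triggered, and say when the row 1 restriction ends after a recurrence, because row 1 gives no later release.

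A site letter or the next amendment would do. For an affected patient the cost is about 2 extra infusion hours at Cycle 4 Day 1. If the sponsor kept the restriction through Cycle 12, it would be up to 9 Day 1 infusions × 2 hours = 18 hours. There is no analysis cost.

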**7.1.2 Lenalidomide (IMP)**

LEN (generic) as sourced from commercially available drug suppliers will be provided centrally. Patients will self-administer a starting dose of 25 mg oral daily on Days 1–21 of each cycle until cycle 12 or discontinuation. Treatment with LEN may be modified and/or de-escalated from 25 mg to 5 mg based upon clinical and laboratory findings. Detailed dose modification guidelines to manage hematological and/or other toxicities are provided in the [Section 7.3.2](#).

Patients must be counselled on the reproductive risks associated with LEN, at the timepoints according to SoA (see [Section 2](#)).

**7.1.3 Pre-Medication for Tafasitamab Infusions**

IRRs have been reported for patients with R/R DLBCL treated with tafasitamab and there is a potential increased risk of IRRs with higher dose levels of tafasitamab.

To reduce the risk of IRRs, pre-medication is mandatory for the first 4 infusions (doses) of tafasitamab. Pre-medication for patients who do not experience any IRRs to tafasitamab during the first 4 infusions (doses) will be optional for subsequent infusions at the discretion of the investigator. Otherwise, the pre-medication should be continued for subsequent administrations.

It is suggested that pre-medication is administered between 30 minutes and 2 hours prior to the tafasitamab infusions.

The pre-medication may include the following:

- Antipyretics (e.g., acetaminophen [paracetamol] 1000 mg per dose per by [p.o.] or i.v. or equivalent).
- Histamine H1 receptor blockers (e.g., diphenhydramine 25–50 mg per dose i.v. or equivalent).
- Histamine H2 receptor blockers (e.g., cimetidine 300 mg p.o. (except Austria), ranitidine 150 mg tablet p.o. or equivalent).
- Glucocorticosteroids (methylprednisolone 80–120 mg per dose i.v. or equivalent - please refer to [Appendix 9: Equivalent Doses for Corticosteroids](#)).

The investigator may repeat doses of individual agents as required and use other agents, doses and/or formulations in accordance with institutional guidelines. Equivalence for pre-medications includes variations to the stated dose due to the formulations available locally. Any pre-medication given should be reported in the eCRF.

